## 1.0 Protocol Summary

Title	A Pilot Study Evaluating the Feasibility and Usability of ToeFX Light Therapy Device for Mild to Moderate Distal Subungual Onychomycosis (DSO) of the Toenail
Short Title	ToeFX light therapy pilot
Methodology	Open label, prospective, multi-site, multi-investigator
Study Sites	
Hamilton Foot Clinic [name]
 
Bruyere Foot Specialists [name]
 
Wilson Foot Clinic [name]

Number of Study Subjects	100 subjects
Diagnosis and Main Inclusion Criteria	
Healthy males or females who meet the following criteria:
 
 
• are between 18-75 years of age.
 
• have a clinical diagnosis of mild to moderate DSO in the nail of at least one great toe, with 20% to 50% clinical involvement of the target toenail, without dermatophytomas or lunula (matrix) involvement, without lunular or proximal involvement.
 
• exhibit positive mycology results (ie, KOH test and culture of a dermatophyte) from the target great toenail, confirming common dermatophytes such as T. rubrum.
 
• are willing to abstain from any other treatment for onychomycosis for the duration of the pilot study.
 

Study Product and Planned Use	The ToeFX Light Therapy system is intended as a safe, effective and non-invasive treatment for nail fungus.

	This device will be used in accordance with the attached protocol. This study will be an open-label, prospective pilot study. The subjects will be 100 patients with mild to moderate onychomycosis. The purpose of the study is to establish the efficacy of the ToeFX device, which has shown compelling results in in vitro and ex vivo (cadaver) studies but has not been tested in patients.
Primary Endpoint	Technical Success: We will monitor (a) whether subjects attain 3 mm or more of clear nail growth post-treatment (b) whether subjects show mycological cure of their infection, as verified by culturing.
Secondary Endpoints	
 
• Usability and form factor reported by clinicians
 
• Satisfaction with the treatment reported by patients
 

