## 2.2 Procedural workflow

A foot care clinician applies a photosensitizer topically to infected toenails; the toenails are then exposed to the ToeFX light source for about 15 minutes. The patient visits the clinic to repeat the process at intervals of two weeks.

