## 3.0 Study Objectives

This study will be an open-label, prospective pilot study. The subjects will be 100 patients who suffer from DSO. The efficacy of photodynamic therapy for treatment of onychomycosis has been demonstrated in the literature. The purpose of the study is to establish the efficacy of the specific ToeFX device, which has shown compelling results in *in vitro* and *ex vivo* (cadaver) studies but has not been tested in patients. Specifically, we wish to:

1. Determine the safety and efficacy of ToeFX photodynamic therapy in the treatment of distal subungual onychomycosis of the toenail.
2. Determine the number of treatments required to clear the nail and to cure the fungus.
3. Finalize the treatment protocol, device design and user interface.
4. Test re-infection or recurrence of fungus post-treatment.

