### 3.2 Study Design

Study Type:	Interventional (clinical trial)
Actual Enrollment:	100 participants
Masking:	None (Open Label)
Primary Purpose:	Treatment
Study Start Date:	Immediately upon approval by Health Canada

Arm	Intervention/treatment
Arm 1 Red light only	Core technology. Formulation and red light only. Apply photosensitizer; allow to penetrate for 15 minutes; apply red light for 15 minutes.
Arm 2 Red and blue light	Apply photosensitizer; place foot under blue light and allow to penetrate for 15 minutes. Apply red light for 15 minutes.

Arm 1 will test the core technology of the ToeFX system; this study reproduces protocols described in the literature (see ‘Previous Studies’ in Section 6.02). Arm 2 pairs the core technology with application of blue light. After application of the formulation, the nail is exposed to blue light at a wavelength of 450-470 nm and an intensity of 200 mW/cm^2. The blue light has no effect on the photosensitizer; however, several research groups have confirmed that exposure to mild blue light can have anti-inflammatory effects that would improve patient

outcomes (see ‘Previous Studies’ in Section 6.02). We will assess whether inclusion of blue light in the protocol affects the clinical outcome.

Debridement should be done prior to each treatment. Debridement should not be carried out more proximally than the most proximal margin of the dystrophic nail, as this can interfere with assessment of clear nail area attributable to the device intervention. Clinician should debride the nail and apply the photosensitizer formula and let it penetrate for 15 minutes, then if applicable apply the blue light (450-470 nm). Apply the red light (640 nm) for 15 minutes. The treatment is administered 12 times over the course of 1 year.

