### **3.4 Outcome Measures**

Clear nail: The specifications for clear nail are described below. The 95% one-sided confidence interval (i.e., lower bound only) around the observed response rate as described below should be  $\geq 50\%$ .

We will monitor whether subjects attain 3 mm or more of clear nail growth post-treatment. We will verify by taking a photograph prior to every treatment to assess the change in millimeters (mm) of clear nail bed. Millimeters (mm) of clear nail from the base of the toenail will be determined from digital photographs of the toenail and verified via software. The change in mm of clear nail bed will be calculated as the difference in mm of clear nail bed from baseline measurement to the measurement at the end of the procedure administration phase.

An increase in mm of clear nail between the two measurement points indicates that the toenail has improved and is positive for study success. A decrease in mm of clear nail between the two measurement points indicates that the toenail has worsened and is negative for study success.

Individual toenail success criterion is defined as 3 millimeter (mm) or more of clear nail growth as evaluated relative to baseline.

Length of the unaffected part of the target nail is measured in millimeters along the midpoint from the nail fold to the proximal border of the affected part (lowest point affected) along the midpoint of the target nail. Change from Baseline is: (Baseline value subtracted from 6-month treatment value). P-value shall be based on analysis of variance (ANOVA) with treatment and pooled center. Statistics will be provided for the adjusted least square mean.

To ensure adequate photographic quality and to maximize our ability to compare photographs across timepoints and across subjects, a standardized photography protocol will be put in place. Photographs shall be of high quality and high resolution. An internal scale (e.g. ruler) will be included in all images to allow objective measurement of millimeters of clear nail regardless of magnification of the image.

**Mycology:** Among toenails which are deemed responders based on the “clear nail” criteria, we will also assess for negative mycology (negative stain with concurrent negative culture, or two negative cultures from the same nail).

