### **3.6 Data Analysis**

- Descriptive statistical analysis to analyze degree of response (e.g., complete response or clearing, >75% clear, 50-75% clear).
- Increase in clear nail at each timepoint of evaluation after the last treatment
- Increase in clear nail as a function of the number of treatments

To evaluate the overall response rates, we plan to ensure that the study report be presented in a tiered fashion, citing the success rate for the subjects exhibiting mycological cure concurrent with clear nail, with separate presentation of the data for subjects exhibiting mycological cure with residual nail dystrophy.

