## **4.0 Study Procedures**

### **4.1 Patient Recruitment and Screening**

Potential study subjects will be identified by the co-investigators or any sub-investigators. It is anticipated that surgical consults will be the primary source of study candidates. Clinicians will ask patients who present with onychomycosis if they are interested in participating in the research trial; those who are interested will be assessed by the clinician for their compatibility with the inclusion/exclusion criteria. Patients that meet all criteria will be asked to submit a nail sample for mycological culturing. This initial review of existing patient information may be performed prior to subject consent; however, no protocol-driven tests or procedures may be performed until after informed consent has been obtained. If the subject shows positive mycology, he/she will be contacted via phone within 2 weeks and asked to sign an informed consent form in person, where a clinician will be present to answer any questions. If the patient is satisfied and has no questions, the treatments may commence at the clinic during the same visit. Research participants will remain in the study for one year.

For the occasional non-English speaking study participant, an on-site translator will be provided at the clinic at the expense of the Sponsor. Informed consent will be treated as an ongoing

process throughout a study. For those who understand English but cannot read, talk, or write, the investigator will provide the necessary support to ensure the subject's ongoing comprehension of new information that may become available during the study.

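### The treatment course is stated two incompatible ways, so the week of the 3 mm readout is undefined and, on one reading, recurrence cannot be assessed

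*Combined protocol and SAP*

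**What the plan says.** On the course of treatment, section 3.2 states: "The treatment is administered 12 times over the course of 1 year". Section 2.1 says the same. Section 2.2 states: "The patient visits the clinic to repeat the process at intervals of two weeks".

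On the time of measurement, the summary (section 1.0) gives the first part of the primary endpoint as "whether subjects attain 3 mm or more of clear nail growth post-treatment", with no week. Section 3.4 takes the change in clear nail "from baseline measurement to the measurement at the end of the procedure administration phase" and sets individual success at 3 mm over baseline. A later paragraph of section 3.4, on nail length along the midpoint and the ANOVA, reads: "Change from Baseline is: (Baseline value subtracted from 6-month treatment value". The mycology paragraph of section 3.4 gives no assessment time.

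On follow-up, section 4.1 states: "Research participants will remain in the study for one year". Section 6.5.2 describes a 52-week study. The fourth objective in section 3.0 is "Test re-infection or recurrence of fungus post-treatment", and section 3.6 plans to report "Increase in clear nail at each timepoint of evaluation after the last treatment". The follow-up paragraph of section 3.4 bases follow-up on a nail regrowth time of about 6 months, says longer is useful for recurrence, and counts dropouts as failures.

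**The concern.** The responder rule has a fixed threshold (3 mm) and a fixed target (a one-sided 95% lower bound of at least 50%), but its date is tied to an event whose own date is contradictory. A fixed growth threshold is easier to reach the longer the nail has had to grow, so the readout week is part of the definition of success. Sites or the analyst could follow different statements and obtain different response rates. In an open-label trial that choice could also be made with the results in view.

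A stated objective is at stake too. Recurrence needs time off treatment, and whether the trial has any depends on which schedule statement is followed.

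**Working it through.** **Inputs.** 12 sessions (sections 2.1 and 3.2); a two-week interval (section 2.2) or one year for the whole course (sections 2.1 and 3.2); 52 weeks in the study (sections 4.1 and 6.5.2); about 6 months for follow-up and a 3 mm threshold (section 3.4). Assumptions: session 1 is at week 0, sessions are evenly spaced, and 6 months is 26 weeks.

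**Can the two schedule statements both hold?** Twelve sessions two weeks apart end at 11 × 2 = week 22, or week 24 if the last interval is counted. A two-week interval kept up for 52 weeks gives 52/2 = 26 sessions, or 27 counting week 0. Neither gives 12 sessions over a year, so the plan's own figure is not reproduced.

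**What each reading implies.** The one-year course is worked with two spacings: 52/12 = 4.33 weeks, and 52/11 = 4.73 weeks (last session on week 52). Last session = 11 × spacing. Time left = 52 − last session. Growth rate needed = (3 mm ÷ week of readout) × 52/12.

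| Quantity | Every two weeks | One year, 4.33-week spacing | One year, 4.73-week spacing |
|---|---|---|---|
| Last session (week) | 22 | 47.7 | 52 |
| Sessions given by week 26 | 12 | 6, or 7 counting one due on week 26 | 6 |
| Weeks left in the study | 30 | 4.3 | 0 |
| Last session + 26 weeks | 48 | 73.7 | 78 |
| Growth needed for 3 mm at last session (mm/month) | 0.59 | 0.27 | 0.25 |

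**The 6-month value.** Counted from baseline it is week 26. That is 26 − 22 = 4 weeks after the last session on the two-week reading, and about halfway through the course on the one-year reading. The rate needed for 3 mm by week 26 is 0.50 mm/month.

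**Effect on the responder criterion.** Between week 22 and week 52 the average growth needed for 3 mm changes by a factor of 52/22 = 2.4. For scale, with all 100 subjects analysed together, an exact lower bound of at least 50% needs 59 responders. That hurdle stays fixed while the difficulty of becoming a responder moves.

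**Recurrence.** Six months after the last session is week 48 on the two-week reading, inside the study. On the one-year reading it is week 73.7 to 78, outside it.

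**Images and samples.** Section 3.4 photographs the nail before every treatment and also calls for a measurement when treatment ends; section 3.1 mentions photographs before and after; section 3.6 presupposes evaluations following the last session. None of these gives a date for an image after treatment 12.

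**The case against.** The strongest reply is that one reading is largely coherent. Twelve two-weekly sessions end at week 22 to 24, close to 6 months. A further 6 months of follow-up then ends at about week 48 to 50, inside the 52 weeks, with room for the recurrence objective and the post-treatment evaluations. This stands: the serious harm is confined to the one-year reading. It does not remove the problem, because the one-year statement appears twice, including in Study Design, and no visit schedule overrides it.

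A reader might infer three stronger points that the documents do not support.

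- *That the primary endpoint itself is given two dates.* The 3 mm response is tied to the end of treatment. The 6-month wording sits in a separate paragraph on the continuous change and its ANOVA, and can be read as a second analysis. The text does not clearly separate the two, since both concern change in clear nail from baseline, but the secure conflict for the responder rate is the treatment schedule. If the 6-month value means 6 months after treatment, further dates arise (week 48, or 73.7 to 78), which again shows that it needs defining.
- *That the one-year reading leaves no post-treatment time at all.* Zero weeks is the extreme; 4.33-week spacing leaves 4.3 weeks. Either is far short of 6 months.
- *That no photograph follows the last treatment.* Sections 3.1, 3.4 and 3.6 intend later images. They do not date them.

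It may also seem that moving the readout to week 52 settles everything. It does not. If session 12 falls on week 52, that readout does not follow the full course. On the two-week reading it would change the question to response 30 weeks off treatment.

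**Conclusion.** The point holds as an internal inconsistency. The two schedule statements cannot both be true of evenly spaced sessions, and they place the 3 mm readout at week 22 or at about weeks 48 to 52, a gap of 25.7 to 30 weeks. The 6-month value in the ANOVA is nearly an end-of-treatment value on one reading and a mid-course value on the other. Objective 4 and the post-treatment analysis can be addressed on the two-week reading and cannot on the one-year reading.

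The arithmetic rests on even spacing from week 0 and on counting 6 months from baseline. The direction of the effect on the response rate is not known: a later readout makes 3 mm easier to reach but gives more time for dropouts, who count as failures. No view is taken here on which schedule is right. Because the date of the primary endpoint and the testability of a stated objective both depend on it, this should be settled before any data are analysed.

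**What to change.** 1. The sponsor must reconcile sections 2.1 and 3.2 with section 2.2 on the treatment schedule.
2. In section 3.4, name one primary assessment at a fixed week counted from first treatment, after the last session of the reconciled course and within the 52 weeks. Use it for the 3 mm response, the mm change and mycology. If the 6-month value differs, report it as secondary and say what it is counted from. If the reconciled course runs to week 52 itself, no later visit fits, and the stated one-year participation must be reconciled as well.
3. Require a photograph with the internal scale and a mycology sample at that visit.
4. If the reconciled course leaves about 6 months inside the 52 weeks, add a photograph and mycology at exit, and define recurrence as positive mycology at exit after negative mycology at the primary assessment. If it does not, remove objective 4 and the post-treatment analysis from what the trial will conclude.

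The cost is amendment wording and one or two dated assessments, within the existing year unless the course fills it. The choice of week has consequences: the 3 mm threshold needs 0.25 mm/month at week 52 against 0.59 at week 22, while a later week can add dropout failures. The week must therefore be fixed before data are seen.

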#### Inclusion Criteria

We are seeking otherwise healthy males or females who meet the following criteria:

- are between 18-75 years of age.
- have a clinical diagnosis of mild to moderate DSO in the nail of at least one great toe, with 20% to 50% clinical involvement of the target toenail, without dermatophytomas or lunula (matrix) involvement, without lunular or proximal involvement.
- exhibit positive mycology results (i.e., KOH test and culture of a dermatophyte) from the target great toenail, confirming common dermatophytes such as *T. rubrum*.

- are willing to refrain from using polish or other medication on treated toenails or on the skin immediately adjacent to the toenails during the treatment period unless directed to do so by the investigator.
- are willing to refrain from using topical steroids or topical antifungals on toenails or the skin immediately adjacent to the toenails or systemic antifungals for the duration of the study.
- are willing to provide signed and dated written voluntary informed consent in English before any protocol-specific procedures are performed.
- are able to complete the study and comply with study instructions.

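### The between-arm test of change in clear nail (mm) leaves out baseline clear-nail length, which is already measured on every subject; adding it as a covariate costs one degree of freedom and can only help precision beyond that.

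*Combined protocol and SAP*

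**What the plan says.** Section 3.4 (Outcome Measures) defines the measurement: "Length of the unaffected part of the target nail is measured in millimeters along the midpoint from the nail fold to the proximal border", that is, to where the diseased portion begins. The outcome is a change score: "Change from Baseline is: (Baseline value subtracted from 6-month treatment value". The test is "P-value shall be based on analysis of variance (ANOVA) with treatment and pooled center", followed by "Statistics will be provided for the adjusted least square mean". No covariate is named for that adjustment, so on the text it is for center alone. Section 3.6 (Data Analysis) adds descriptive summaries and no further model.

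A baseline value exists for every treated subject: "We will verify by taking a photograph prior to every treatment to assess the change in millimeters (mm) of clear nail bed". Entry requires a target nail "with 20% to 50% clinical involvement of the target toenail" (Section 3.5).

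Section 3.2 sets up the two arms and commits to a comparison: "We will assess whether inclusion of blue light in the protocol affects the clinical outcome". I read the treatment term in the ANOVA as this arm factor. It is the only between-arm p-value that the plan names.

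**The concern.** A baseline measurement of the outcome is usually the first covariate to consider for a change score. Here there is also a physical reason to expect a relation. Clear length is measured up to the affected border, so the gain from clearing cannot exceed the length affected at the start, and entry allows that to vary widely between subjects. If baseline and change are correlated, a model without baseline leaves that variation in the error term, and any chance difference between the arms at baseline passes into the estimated effect.

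Precision matters because the 100 subjects were justified in Section 3.3 only by cure rate against a published control. Nothing in the documents sizes the study for the blue-light question.

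**Working it through.** **Inputs from the documents.** Outcome: 6-month value minus baseline. Model terms: treatment and pooled center. Total N: 100. Not given: SD of clear length at either visit, their correlation, allocation ratio, alpha or power. The plan states no figure for this comparison, so there is none to reproduce.

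**Assumptions.** 50 per arm, two-sided alpha 0.05, normal approximation. Let ρ be the correlation of baseline with the 6-month value, and k the follow-up SD divided by the baseline SD σ.

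**Step 1: what the present model can detect.** The difference detectable with 80% power is (1.960 + 0.842) × √(2/50) = 0.56 SD of change.

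**Step 2: variance ratio.**

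- Change-score ANOVA: σ²(1 + k² − 2ρk).
- ANCOVA with baseline: σ²k²(1 − ρ²). This is the same whether the response is the change or the 6-month value.
- Ratio: (1 − ρ²)k² / (1 + k² − 2ρk), which equals 1 − r², where r is the correlation of baseline with change.
- With k = 1 this reduces to (1 + ρ)/2. The ratio is exactly 1 (no gain) when ρk = 1.

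**Step 3: numbers.** The power column takes a difference for which ANOVA has 80% power and computes Φ(2.802/√ratio − 1.960).

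| k | ρ | Ratio | Variance reduction | ANCOVA power |
|---|---|---|---|---|
| 1 | 0.3 | 1.3/2 = 0.65 | 35% | 93.5% |
| 1 | 0.5 | 1.5/2 = 0.75 | 25% | 89.9% |
| 1 | 0.7 | 1.7/2 = 0.85 | 15% | 86.0% |
| 1 | 0.9 | 1.9/2 = 0.95 | 5% | 82.0% |
| 1.5 | 0.3 | 2.0475/2.35 = 0.871 | 13% | 85.1% |
| 1.5 | 0.5 | 1.6875/1.75 = 0.964 | 4% | 81.4% |
| 1.5 | 0.7 | 1.1475/1.15 = 0.998 | 0.2% | 80.1% |
| 2 | 0.5 | 3/3 = 1.00 | 0% | 80.0% |

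**Step 4: how far the ceiling alone carries the argument.** A simulation capped each nail's gain at its affected length. It assumed mean nail lengths of 14 mm (SD 1.5) or 18 mm (SD 2), involvement uniform between 20% and 50% and applied to length, and uncapped growth averaging 3, 5 or 8 mm with SD 2. None of these lengths or growth figures is in the documents. The correlation r ran from −0.03 to −0.45, a variance reduction of about 0% to 20%. The small values arise where few nails reach full clearance. With every nail exactly 14 mm long, the reduction ran from 2% to 88%, so variation in nail length between subjects weakens the link considerably.

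**Step 5: cost.** One degree of freedom. With 100 subjects, two arms and three center levels, the residual degrees of freedom go from 100 − 1 − 1 − 2 = 96 to 95.

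**The case against.** An unadjusted change-score ANOVA is a valid test under random allocation, this is a pilot, and the choice of ANCOVA is one of efficiency. That stands, and it limits the weight of the point. Four stronger readings are tempting and are not supported.

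- **That a reduction of at least 15% is assured.** The 15% to 35% range (ρ from 0.7 to 0.3) needs equal variances at both visits. Entry criteria restrict the baseline range, while follow-up mixes responders and non-responders, so k could exceed 1. The gain can then vanish.
- **That baseline clear length is prognostic by construction.** The gain is bounded by affected length, whereas the covariate is clear length, and a long clear segment may simply belong to a long nail. Section 3.3 also describes the 20% to 50% as involvement of nail area, not midline length. A relation is likely, not guaranteed.
- **That the ANOVA discards dropouts and a repeated-measures model should rescue them.** The plan is silent on missing mm values. The follow-up paragraph of Section 3.4 counts dropouts as failures precisely because loss may depend on outcome. A mixed model would need a missing-at-random assumption that fits poorly with that.
- **That the study's success criteria are weakened.** They rest on the responder rate, mycology and the published cure rate, not on this ANOVA.

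It can also be said that, with no randomisation described in Section 3.2, baseline imbalance might be systematic. That is right, and a single covariate would not cure it.

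**Conclusion.** The point holds as a modest, nearly free improvement to one analysis. Section 3.4 omits a covariate that is already in hand, and no other section supplies it. In large samples ANCOVA is never less precise than the change-score ANOVA, apart from the one degree of freedom.

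The benefit is a range, because ρ and k are unknown: 5% to 35% less variance with k = 1 and ρ from 0.9 to 0.3, and about 0% to 13% with k = 1.5 and ρ from 0.7 to 0.3. The power figures rest further on an assumed 50 per arm. Adjustment for baseline imbalance is meant for chance differences. If the arms are not randomised, the adjusted estimate is not thereby made unbiased.

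**What to change.** Replace the model sentence in Section 3.4 with wording such as:

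> ANCOVA of change in clear nail (mm) from baseline to 6 months, with treatment, pooled center and baseline clear-nail length as covariate; baseline-adjusted least square mean difference between arms with 95% CI.

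The timepoint must be reconciled at the same time. Section 3.4 measures change both at 6 months and at the end of the procedure administration phase. Sections 2.1 and 3.2 spread the 12 treatments over 1 year, while Section 2.2 has visits every two weeks. Until these agree, the outcome of the model is not uniquely defined.

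The cost is an edit to the analysis text, made before outcome data are examined, and one residual degree of freedom. No new measurement is needed.

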### Exclusion Criteria

The following populations are excluded from the study:

- patients with glucose-6 phosphate dehydrogenase (G6PD) deficiency or hypersensitivity/allergies to methylene blue.
- females who are pregnant, plan to become pregnant during the study, or are nursing a child.
  - As the effect on an unborn child is unknown, all female research participants of childbearing potential must take a urine pregnancy test at screening and every 3 months (12 weeks) for the duration of the Study.
  - Hormonal methods and/or IUD must be in use at least 30 days prior to first Study intervention; barrier methods must be in use at least 14 days prior to Study intervention; vasectomy must be completed 3 months prior to first Study intervention; or in the alternative a 0 sperm count will suffice.
- persons who are hypersensitive to topical creams, ointments, medications, or surfactants.
- persons who have received systemic antifungal therapy for any reason within 3 months, or topical antifungal therapy on the toenails or skin immediately adjacent to the toenails within 3 weeks prior to the start of the study.
- persons who have received an investigational drug within 4 weeks of the first dose of study product, or who are scheduled to receive an investigational drug other than the study product during the study.
- persons who have participated in a clinical trial for the systemic treatment of onychomycosis of the toenails within 6 months prior to the first dose of study product.
- persons who are not prepared to give up use of any nail cosmetic products for the duration of the study.
- persons who have any known immunodeficiency or history of malignancy in the last 4 years, excluding nonmelanoma skin cancer.
- persons currently suffering from any disease or condition, that could include abnormal laboratory tests, and/or who are currently using medication which in the opinion of the investigator may affect the evaluation of the study product or place the subject at undue risk.

- persons with psoriasis, lichen planus, or other medical conditions known to induce nail changes, other abnormalities or can causes of nail breakdown that can predispose to secondary fungal infection. Trauma from ill-fitting shoes, running, or overly aggressive nail care can also induce changes visually indistinguishable from onychomycosis that could result in a clinically abnormal toenail.

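### Mycological cure can be scored with no treatment-free interval and on cultures alone, so it cannot be told apart from short-term suppression or debridement

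*Combined protocol and SAP*

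**What the plan says.** The protocol summary (section 1.0) makes mycology half of the primary endpoint: "whether subjects show mycological cure of their infection, as verified by culturing". Microscopy is not mentioned there.

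Section 3.4 gives the working definition. It first says who is tested: "Among toenails which are deemed responders based on the “clear nail” criteria, we will also assess for negative mycology". It then defines the result as "negative stain with concurrent negative culture, or two negative cultures from the same nail". It sets no sampling day, no minimum time since the last session, and no separation between the two cultures. The clear-nail status that opens the way to mycology is read when the course of sessions ends. The same section also computes change from baseline at 6 months.

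Entry is stricter. Under the inclusion criteria in 3.5, subjects must "exhibit positive mycology results (i.e., KOH test and culture of a dermatophyte) from the target great toenail". The exclusion criteria in 3.5 bar "topical antifungal therapy on the toenails or skin immediately adjacent to the toenails within 3 weeks prior to the start of the study".

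On timing of treatment, section 2.2 says: "The patient visits the clinic to repeat the process at intervals of two weeks". Sections 2.1 and 3.2 say: "The treatment is administered 12 times over the course of 1 year". Section 4.1 keeps participants in the study for one year. Section 3.2 calls for debridement before each session.

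**The concern.** There are two separate gaps, and both run in the same direction.

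The first is timing. A specimen taken at or shortly after a session comes from a nail that has just been debrided, painted with photosensitizer and irradiated. A negative result then may mean that the organism is gone, that it is temporarily suppressed, or that the material which would have grown was cut away. The protocol gives no way to tell these apart.

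The second is the test. The two-culture route needs no microscopy, and both cultures may come from one visit. A subject who entered on two positive tests can be declared cured with one of them never repeated, or repeated and still positive.

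The Follow-up paragraph of 3.4 names eradication of the organism as the goal, so component (b) might not measure what it is meant to measure. A false negative can only add cures. It would pass into the top reporting tier of 3.6, and a later positive would look like recurrence, which is objective 4 in section 3.0. Both arms in 3.2 receive photosensitizer and red light, and the control in 3.3 is published data, so comparing the arms would not expose the problem.

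**Working it through.** **No plan figure to reproduce.** The protocol states no target or error rate for mycological cure. The 50% lower bound in 3.4 is set for clear nail, and this point does not depend on the sample size of 100.

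**Step 1: entry against cure.**

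| | Microscopy | Culture | Timing rule |
|---|---|---|---|
| Entry (3.5) | KOH positive required | Positive required | None on the specimen; 3 weeks without topical antifungals before study start |
| Cure, route 1 (3.4) | Negative stain | Negative, concurrent | None |
| Cure, route 2 (3.4) | Not required | Two negative, same nail | None |
| Cure, section 1.0 | Not mentioned | Culture | None |

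**Step 2: days from last session to sample.** Inputs are the two schedule statements, the two reading points in 3.4, and a 52-week year (364 days), with session 1 on day 0.

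- Sample at the final session visit, after treatment: 0 days on any schedule. Just before that session, the gap is to the previous one: 14 days if two-weekly, about 30 to 33 days if spread over the year (spacings below).
- Twelve two-weekly sessions: the last is on day 11 × 14 = 154. A 6-month sample at 26 × 7 = 182 days is 182 − 154 = 28 days later.
- Twelve sessions, one every 364/12 = 30.3 days: session 7 falls on day 6 × 30.33 = 182. A 6-month sample is 0 days after it, or about 30 days after session 6 if taken first. The last session is on day 11 × 30.33 = 333.7, so a day-364 sample is 30.3 days later.
- Twelve sessions from day 0 to day 364, spacing 364/11 = 33.1 days: session 6 falls on day 5 × 33.09 = 165.5, so a 6-month sample is 16.5 days later. A day-364 sample, taken after the last session, is at 0 days.

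The permitted gap thus runs from 0 to about 33 days. Twelve two-weekly sessions end at week 22, not at one year, so the schedule statements have to be reconciled before a sampling day can be fixed.

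**Step 3: how much the test rule could matter (illustration only).** The documents give no miss rates. Let p be the true cure proportion among nails tested, and q the chance that an uncured nail passes the rule. Apparent cure = p + (1 − p) × q. Assume p = 0.30, a culture miss rate of 0.30 and a stain miss rate of 0.10.

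- Stain and culture, independent errors: q = 0.30 × 0.10 = 0.03; 0.30 + 0.70 × 0.03 = 32.1%.
- Two independent cultures: q = 0.30 × 0.30 = 0.09; 0.30 + 0.70 × 0.09 = 36.3%.
- Two fully correlated cultures (the extreme for one visit): q = 0.30; 0.30 + 0.70 × 0.30 = 51.0%.

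Over assumed true cure of 15–50%, culture miss of 10–50% and stain miss of 10–30%, the overstatement is about 0.5 to 13 points for stain plus culture and 5 to 43 points for fully correlated cultures. The ranges are wide because the inputs are guesses. They show that the rule can matter, not that it does.

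**The case against.** The strongest reply is that carry-over is only a hypothesis. Section 2.1 says the photoreaction stops when the light goes off, and no section says that residual dye or recent treatment suppresses culture. That stands: carry-over would need residual dye, living but suppressed fungus, or removal of material by debridement, and the documents neither show nor exclude these.

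A reader might infer that the plan breaches its own wash-out. It does not. The 3 weeks in 3.5 is an eligibility rule about earlier topical antifungals. It does not concern the photosensitizer or light, and it is counted back from study start, not from the baseline specimen, which 4.1 collects at screening. It serves only as an analogy.

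A reader might also infer that mycology samples during treatment will all fall within 3 weeks of a session. No mycology during treatment is scheduled. Photographs are taken before each session, 3.4 has a 6-month reading and mentions about 6 months of follow-up, and 3.6 mentions evaluations after the last treatment. Some readings have an adequate gap. None of these passages, however, sets the mycology sample.

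Finally, no passage establishes that a KOH-positive nail with two negative cultures is still infected, and section 1.0 is only a summary. Both are fair. The point is narrower: the protocol relies on microscopy to confirm infection and then allows cure without it.

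**Conclusion.** The concern holds in a limited form. The rules in 1.0 and 3.4 allow component (b) to be met at the end of treatment, with no treatment-free interval, by two cultures that may share a visit and with no microscopy. A just-treated or KOH-positive nail can be scored as cured, and any resulting error favours the device.

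The problem is permitted, not certain. Its size is unknown, and the percentages above rest wholly on assumed miss rates; a reader should not take them as an estimate of false cures in this trial. Its reach is also limited: mycology is read only in nails that have already gained at least 3 mm of clear nail, and dropouts count as failures. This is a worthwhile, low-cost correction to an endpoint definition, not a defect that invalidates the study.

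**What to change.** In 3.4:

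- State that the specimen deciding mycological cure is taken after a specified treatment-free interval since the last session and debridement. At least 3 weeks is one candidate, by analogy with the topical-antifungal rule at entry; the sponsor should give its reason for whatever interval it chooses.
- Define cure as negative KOH and negative dermatophyte culture on the same specimen. If the two-culture route is kept, require separate visits and no positive KOH.
- Label any earlier mycology as descriptive.

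Align the endpoint wording in section 1.0 with this definition. Reconcile the schedule statements in 2.1, 2.2 and 3.2 with the one-year participation in 4.1, so that the sampling day can be set. This point takes no position on which schedule is right.

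The cost is small, since KOH and culture are already in use and only clear-nail responders are sampled. The cure rate may be read slightly later and come out lower. If sessions run to the end of the year, responders may need one later sample and slightly longer participation.
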